8.3.1.1. Reporting SAEs to Pfizer Safety

All SAEs occurring in a participant during the active collection period are reported to Pfizer Safety on the Vaccine SAE Reporting Form immediately upon awareness and under no circumstance should this exceed 24 hours, as indicated in [Appendix 3](#). The investigator will submit any updated SAE data to the sponsor within 24 hours of it being available.

SAEs occurring in a participant after the active collection period has ended are reported to Pfizer Safety if the investigator becomes aware of them; at a minimum, all SAEs that the investigator believes have at least a reasonable possibility of being related to investigational product must be reported to Pfizer Safety.

8.3.1.2. Recording Nonserious AEs and SAEs on the CRF

All nonserious AEs and SAEs occurring in a participant during the active collection period, which begins after obtaining informed consent as described in [Section 8.3.1](#), will be recorded on the AE section of the CRF.

The investigator is to record on the CRF all directly observed and all spontaneously reported AEs and SAEs reported by the participant.

8.3.2. Method of Detecting AEs and SAEs

The method of recording, evaluating, and assessing causality of AEs and SAEs and the procedures for completing and transmitting SAE reports are provided in [Appendix 3](#).

Care will be taken not to introduce bias when detecting AEs and/or SAEs. Open-ended and nonleading verbal questioning of the participant's parent(s)/legal guardian(s) is the preferred method to inquire about AE occurrences.

8.3.3. Follow-up of AEs and SAEs

After the initial AE/SAE report, the investigator is required to proactively follow each participant at subsequent visits/contacts. For each event, the investigator must pursue and obtain adequate information until resolution, stabilization, the event is otherwise explained, or the participant is lost to follow-up (as defined in [Section 7.3](#)).

In general, follow-up information will include a description of the event in sufficient detail to allow for a complete medical assessment of the case and independent determination of possible causality. Any information relevant to the event, such as concomitant medications and illnesses, must be provided. In the case of a participant death, a summary of available autopsy findings must be submitted as soon as possible to Pfizer Safety.

Further information on follow-up procedures is given in Appendix 3 ([Section 10.3](#)).

8.3.4. Regulatory Reporting Requirements for SAEs

Prompt notification by the investigator to the sponsor of an SAE is essential so that legal obligations and ethical responsibilities towards the safety of participants and the safety of a study intervention under clinical investigation are met.

The sponsor has a legal responsibility to notify both the local regulatory authority and other regulatory agencies about the safety of a study intervention under clinical investigation. The sponsor will comply with country-specific regulatory requirements relating to safety reporting to the regulatory authority, IRBs/ECs, and investigators.

Investigator safety reports must be prepared for suspected unexpected serious adverse reactions (SUSARs) according to local regulatory requirements and sponsor policy and forwarded to investigators as necessary.

An investigator who receives an investigator safety report describing an SAE or other specific safety information (eg, summary or listing of SAEs) from the sponsor will review and then file it along with the IB and will notify the IRB/EC, if appropriate according to local requirements.

8.3.5. Exposure During Pregnancy or Breastfeeding, and Occupational Exposure

[figure not shown]
[figure not shown]
Exposure to the investigational product under study during pregnancy or breastfeeding and occupational exposure are reportable to Pfizer Safety within 24 hours of investigator awareness.

8.3.5.1. Exposure During Pregnancy

An EDP occurs if:

- A female participant is found to be pregnant while receiving or after discontinuing study intervention.
- A male participant who is receiving or has discontinued study intervention exposes a female partner prior to or around the time of conception.
- A female is found to be pregnant while being exposed or having been exposed to study intervention due to environmental exposure. Below are examples of environmental exposure during pregnancy:
 - A female family member or healthcare provider reports that she is pregnant after having been exposed to the study intervention by ingestion, inhalation, or skin contact.
 - A male family member or healthcare provider who has been exposed to the study intervention by ingestion, inhalation, or skin contact then exposes his female partner prior to or around the time of conception.

PFIZER CONFIDENTIAL

The investigator must report EDP to Pfizer Safety within 24 hours of the investigator's awareness, irrespective of whether an SAE has occurred. The initial information submitted should include the anticipated date of delivery (see below for information related to termination of pregnancy).

- If EDP occurs in a participant or a participant's partner, the investigator must report this information to Pfizer Safety on the Vaccine SAE Reporting Form and an EDP Supplemental Form, regardless of whether an SAE has occurred. Details of the pregnancy will be collected after the start of study intervention and until study end.
- If EDP occurs in the setting of environmental exposure, the investigator must report information to Pfizer Safety using the Vaccine SAE Reporting Form and EDP Supplemental Form. Since the exposure information does not pertain to the participant enrolled in the study, the information is not recorded on a CRF; however, a copy of the completed Vaccine SAE Reporting Form is maintained in the investigator site file.

Follow-up is conducted to obtain general information on the pregnancy and its outcome for all EDP reports with an unknown outcome. The investigator will follow the pregnancy until completion (or until pregnancy termination) and notify Pfizer Safety of the outcome as a follow-up to the initial EDP Supplemental Form. In the case of a live birth, the structural integrity of the neonate can be assessed at the time of birth. In the event of a termination, the reason(s) for termination should be specified and, if clinically possible, the structural integrity of the terminated fetus should be assessed by gross visual inspection (unless preprocedure test findings are conclusive for a congenital anomaly and the findings are reported).

Abnormal pregnancy outcomes are considered SAEs. If the outcome of the pregnancy meets the criteria for an SAE (ie, ectopic pregnancy, spontaneous abortion, intrauterine fetal demise, neonatal death, or congenital anomaly in a live-born baby, a terminated fetus, an intrauterine fetal demise, or a neonatal death), the investigator should follow the procedures for reporting SAEs. Additional information about pregnancy outcomes that are reported to Pfizer Safety as SAEs follows:

- Spontaneous abortion including miscarriage and missed abortion;
- Neonatal deaths that occur within 1 month of birth should be reported, without regard to causality, as SAEs. In addition, infant deaths after 1 month should be reported as SAEs when the investigator assesses the infant death as related or possibly related to exposure to the study intervention.

Additional information regarding the EDP may be requested by the sponsor. Further follow-up of birth outcomes will be handled on a case-by-case basis (eg, follow-up on preterm infants to identify developmental delays). In the case of paternal exposure, the investigator will provide the participant with the Pregnant Partner Release of Information

Form to deliver to his partner. The investigator must document in the source documents that the participant was given the Pregnant Partner Release of Information Form to provide to his partner.

8.3.5.2. Exposure During Breastfeeding

An exposure during breastfeeding occurs if:

- A female participant is found to be breastfeeding while receiving or after discontinuing study intervention.
- A female is found to be breastfeeding while being exposed or having been exposed to study intervention (ie, environmental exposure). An example of environmental exposure during breastfeeding is a female family member or healthcare provider who reports that she is breastfeeding after having been exposed to the study intervention by inhalation or skin contact.

The investigator must report exposure during breastfeeding to Pfizer Safety within 24 hours of the investigator's awareness, irrespective of whether an SAE has occurred. The information must be reported using the Vaccine SAE Reporting Form. When exposure during breastfeeding occurs in the setting of environmental exposure, the exposure information does not pertain to the participant enrolled in the study, so the information is not recorded on a CRF. However, a copy of the completed Vaccine SAE Reporting Form is maintained in the investigator site file.

An exposure during breastfeeding report is not created when a Pfizer drug specifically approved for use in breastfeeding women (eg, vitamins) is administered in accord with authorized use. However, if the infant experiences an SAE associated with such a drug, the SAE is reported together with the exposure during breastfeeding.

8.3.5.3. Occupational Exposure

An occupational exposure occurs when, during the performance of job duties, a person (whether a healthcare professional or otherwise) gets in unplanned direct contact with the product, which may or may not lead to the occurrence of an AE.

An occupational exposure is reported to Pfizer Safety within 24 hours of the investigator's awareness, using the Vaccine SAE Reporting Form, regardless of whether there is an associated SAE. Since the information does not pertain to a participant enrolled in the study, the information is not recorded on a CRF; however, a copy of the completed Vaccine SAE Reporting Form is maintained in the ISF.

8.3.6. Cardiovascular and Death Events

Not applicable

8.3.7. Disease-Related Events and/or Disease-Related Outcomes Not Qualifying as AEs or SAEs

Not applicable

8.3.8. Adverse Events of Special Interest

Not applicable

8.3.8.1. Lack of Efficacy

This section is not applicable because efficacy is not expected in the study population.

8.3.9. Medical Device Deficiencies

Medical devices are being provided for use in this study for the purposes of administering the investigational product. In order to fulfill regulatory reporting obligations worldwide, the investigator is responsible for the detection and documentation of events meeting the definitions of deficiencies that occur during the study with such devices.

The definition of a medical device deficiency can be found in [Appendix 8](#).

NOTE: Deficiencies fulfilling the definition of an AE/SAE will also follow the processes outlined in [Section 8.3.3](#) and [Section 10.3](#) of the protocol.

8.3.9.1. Time Period for Detecting Medical Device Deficiencies

Medical device deficiencies or malfunctions of the device that result in an incident will be detected, documented, and reported during all periods of the study in which the medical device is used.

If the investigator learns of any device deficiency at any time after a participant has been discharged from the study, and such incident is considered reasonably related to a medical device provided for the study, the investigator will promptly notify the sponsor.

The method of documenting medical device deficiencies is provided in [Appendix 8](#).

8.3.9.2. Follow-up of Medical Device Deficiencies

All medical device deficiencies involving an AE will be followed and reported in the same manner as other AEs (see [Section 8.3.3](#)). This applies to all participants, including those who discontinue study intervention. The investigator is responsible for ensuring that follow-up includes any supplemental investigations as indicated to elucidate the nature and/or causality of the deficiency.

New or updated information will be recorded on a follow-up form with all changes signed and dated by the investigator.

8.3.9.3. Prompt Reporting of Device Deficiencies to Sponsor

Device deficiencies will be reported to the sponsor within 1 day after the investigator determines that the event meets the protocol definition of a medical device deficiency.

Any device deficiency that is associated with an SAE must be reported to Pfizer Safety within 24 hours upon the investigator's awareness as outlined in [Section 8.3.1.1](#) and [Section 8.3.1.2](#).

The sponsor will be the contact for the receipt of device deficiency information.

Information will be provided to the sponsor as described in the IP manual.

8.3.9.4. Regulatory Reporting Requirements for Medical Device Deficiencies

The investigator will promptly report all device deficiencies occurring with any medical device provided for use in the study in order for the sponsor to fulfill the legal responsibility to notify appropriate regulatory authorities and other entities about certain safety information relating to medical devices being used in clinical studies.

The investigator, or responsible person according to local requirements (eg, the head of the medical institution), will comply with the applicable local regulatory requirements relating to the reporting of device deficiencies to the IRB/EC.

8.3.10. Medication Errors

Medication errors may result from the administration or consumption of the investigational product by the wrong participant, or at the wrong time, or at the wrong dosage strength.

Exposures to the investigational product under study may occur in clinical trial settings, such as medication errors.

[figure not shown]
Safety Event	Recorded on the CRF	Reported on the Vaccine SAE Reporting Form to Pfizer Safety Within 24 Hours of Awareness
Medication errors	All (regardless of whether associated with an AE)	Only if associated with an SAE

Medication errors include:

- Medication errors involving participant exposure to the investigational product;
- Potential medication errors or uses outside of what is foreseen in the protocol that do or do not involve the study participant.

Such medication errors occurring to a study participant are to be captured on the medication error page of the CRF, which is a specific version of the AE page.

PFIZER CONFIDENTIAL

In the event of a medication dosing error, the sponsor should be notified immediately.

Whether or not the medication error is accompanied by an AE, as determined by the investigator, the medication error is recorded on the medication error page of the CRF and, if applicable, any associated AE(s), serious and nonserious, are recorded on an AE page of the CRF.

Medication errors should be reported to Pfizer Safety within 24 hours on a Vaccine SAE Reporting Form **only when associated with an SAE**.

Other examples include, but are not limited to:

- The administration of expired investigational product;
- The administration of an incorrect investigational product;
- The administration of an incorrect dosage;
- The administration of investigational product that has undergone temperature excursion from the specified storage range, unless it is determined by the sponsor that the investigational product under question is acceptable for use.

8.4. Treatment of Overdose

For this study, any dose of investigational product greater than 1 dose of investigational product within a 24-hour time period will be considered an overdose.

Pfizer does not recommend specific treatment for an overdose.

In the event of an overdose, the investigator should:

1. Contact the medical monitor within 24 hours.
2. Closely monitor the participant for any AEs/SAEs.
3. Document the quantity of the excess dose as well as the duration of the overdose in the CRF.
4. Overdose is reportable to Safety **only when associated with an SAE**.

8.5. Pharmacokinetics

Pharmacokinetic parameters are not evaluated in this study.

8.6. Pharmacodynamics

Pharmacodynamic parameters are not evaluated in this study.

8.7. Genetics

Genetics (specified analyses) are not evaluated in this study.

8.8. Biomarkers

Biomarkers are not evaluated in this study.

8.9. Health Economics

Health economics/medical resource utilization and health economics parameters are not evaluated in this study.

8.10. Study Procedures

The study procedures are summarized in the SoA ([Section 1.3](#)). The day of Dose 1 is considered to be Day 1.

Unless specified in the sections below, the order of key procedures within a given a visit may have some flexibility.

8.10.1. Visit 1 (Vaccination 1, Day 1)

Prior to vaccination:

- Obtain a personally signed and dated ICD indicating that the participant's parent(s)/legal guardian(s) has been informed of all pertinent aspects of the study before performing any study-specific procedures.
- Assign a participant number via the IRT.
- Obtain and record the participant's demographic information (including date of birth, sex, race, and ethnicity). The complete date of birth (ie, DD-MMM-YYYY) will be collected as permitted per local regulations to critically evaluate the immune response and safety profile by age.
- Perform a clinical assessment including medical history; record any findings on the medical history CRF.
- Measure and record the participant's temperature as appropriate for the age of the child, according to routine local practice (°F/°C).
- Confirm receipt of 3 or more prior doses of 13vPnC and record the date of prior administration of the most recent (third or fourth) dose of 13vPnC for Cohorts 1 and 2 only. Record the date of administration of the most recent dose of 7vPnC or 13vPnC for Cohorts 3 and 4, if available.

- Perform urine pregnancy test for female participants of childbearing potential (see [Section 8.2.4](#)).
- For participants of childbearing potential, instruct the participant to use appropriate contraceptives until 28 days after administration of investigational product and document the conversation and the participant's affirmation in the participant's source document.
- Ensure and document that all of the inclusion criteria and none of the exclusion criteria are met and that none of the temporary delay criteria are met.
- Assign an investigational product container number via the IRT. This must be the last step before proceeding. A site staff member will prepare the investigational product according to the IP manual.

After investigational product container number assignment:

- Collect a blood sample of approximately 5 mL for Cohorts 1 and 2, and approximately 10 mL for Cohorts 3 and 4, for immunogenicity assessments prior to vaccination.
- Administer a single 0.5-mL injection of 20vPnC into the left leg (option for Cohort 1 only) or left arm.
- Permitted routine pediatric vaccines may be given at the same time as study vaccination according to local or national recommendations (to be administered into a limb other than the site of 20vPnC). However, if feasible, it is recommended that licensed nonstudy vaccines be administered at least 14 days or 28 days (see [Section 6.5.2](#)) before or after 20vPnC administration. The location of the injection of each vaccine administered at Visit 1 (20vPnC and other, if applicable) will be recorded on the CRF.

After vaccination:

[figure not shown]
- Site staff will observe the participant for 30 minutes after vaccination for any reactions. Record any AEs on the CRF and on an SAE form as applicable. Record concomitant medications used to treat SAEs and NDCMCs.
- Issue the participant's parent(s)/legal guardian(s) a measuring device (caliper) to measure injection site reactions in the participant's limb that received the 20vPnC and a digital thermometer to measure temperature, and provide instructions on their use.
- Issue the participant's parent(s)/legal guardian(s) an e-diary (device or application). Provide instructions on use and completion of the e-diary. Ask the participant's parent(s)/legal guardian(s) to complete the e-diary from Day 1 to Day 7, with Day 1 being the day of vaccination.

- Ask the participant's parent(s)/legal guardian(s) to contact the investigator site staff or investigator as soon as possible during the 7-day postvaccination period if the participant has a fever >40.0°C (>104.0°F), redness and/or swelling at the injection site (left leg [option for Cohort 1 only] or left arm) measuring >14 measuring device units (>7 cm), or severe injection site pain (causes limitation of limb movement) to determine if the event requires further assessment by the investigator.
- Ask the participant or the participant's parent(s)/legal guardian(s) to contact the investigator or investigator site staff as soon as possible if any significant illness or medical event (eg, emergency room visit or hospitalization) occurs.
- Provide the parent(s)/legal guardian(s) with the participant contact card containing the study and investigator information (see [Section 10.1.10](#)).
- Inform the participant's parent(s)/legal guardian(s) that the use of prophylactic antipyretic/pain medication, while permitted, is not recommended on the day of 20vPnC administration (before or after vaccination).
- Record AEs, SAEs, and NDCMCs during the visit as described in [Section 8.3](#) and record concomitant medications as described in [Section 6.5.3](#).
- The investigator or an authorized designee completes the CRF and updates the investigational product accountability records.
- The investigator or appropriately qualified designee reviews the e-diary data online at frequent intervals for the 7 days following vaccination to evaluate participant compliance and as part of the ongoing safety review.

8.10.2. Visit 2 (Follow-up: 28 to 42 Days After Visit 1, ie, Study Day 29 to 43)

- Record nonstudy vaccinations administered since Visit 1, as described in [Section 6.5.3](#).
- Perform a contraception check (see [Section 10.4](#)), if applicable (Cohort 3 and Cohort 4 only).
- Ensure and document that the participant continues to be eligible for the study (see [Section 7.2](#) for participant discontinuation/withdrawal) and that the temporary delay criteria for the immunogenicity blood draw are not met.
- Review the participant's e-diary data with the participant's parent(s)/legal guardian(s); collect stop dates of any e-diary events ongoing on the last day that the e-diary was completed and record stop dates in the CRF.
- Collect the e-diary (if applicable).

PFIZER CONFIDENTIAL

- Determine whether any AEs (includes nonserious AEs, SAEs, and NDCMCs) have occurred since the previous visit and follow up on any previously reported events to determine the outcome (ie, record stop dates or confirm if they are still continuing) and record as described in [Section 10.3](#) and record concomitant medications used to treat NDCMCs and SAEs.
- Collect a blood sample of approximately 5 mL for Cohorts 1 and 2, and approximately 10 mL for Cohorts 3 and 4, for immunogenicity (a topical anesthetic is permitted).
- Remind the participant or the participant's parent(s)/legal guardian(s) to contact the investigator or investigator site staff as soon as possible if any significant illness or medical event (eg, emergency room visit or hospitalization) occurs.
- Confirm whether the parent(s)/legal guardian(s) still possesses the participation contact card.
- The investigator or an authorized designee completes the CRF and the source documents.

[figure not shown]
8.10.3. Visit 3 (6-Month Safety Collection [Telephone Contact] – 168 to 196 Days After Visit 1)

- Contact the participant's parent(s)/legal guardian(s) by telephone approximately 6 months after the study vaccination; this contact should be attempted for all participants who have received study vaccination, unless the participant's parent(s)/legal guardian(s) has withdrawn consent.
- Determine whether any SAEs and NDCMCs have occurred since the previous visit and follow up on any previously reported events to determine the outcome (ie, record stop dates or confirm if they are still continuing) and record as described in [Section 10.3](#) and record concomitant medications used to treat NDCMCs and SAEs.
- The investigator or an authorized designee completes the CRF and the source documents.

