On Day 1 of the study (Visit 1), participants will be assessed for eligibility and information will be collected, including medical history and 13vPnC vaccination history. Blood will be collected prior to vaccination for immunogenicity assessments. Participants will receive a single dose of 20vPnC, which will be prepared and administered by a qualified site staff member or designee. Permitted routine pediatric vaccines may be given at the same time as study vaccination according to local or national recommendations, if not feasible to separate from the 20vPnC. Participants will be observed for 30 minutes after vaccination and any reactions occurring during that time will be recorded as adverse events (AEs). The participant's parent(s)/legal guardian(s) will be provided with an electronic diary (e-diary) (or e-diary application), thermometer, and measuring device and instructed to collect prompted local reactions (redness, swelling, and pain at the injection site) and age-applicable systemic events (fever, decreased appetite, drowsiness/increased sleep, and irritability in Cohort 1; and fever, fatigue, headache, muscle pain, and joint pain in Cohorts 2-4) for 7 days following vaccination (Days 1 to 7, where Day 1 is the day of vaccination). Use of antipyretic/pain medications will also be prompted for and collected daily in the e-diary for 7 days following vaccination. The participant's parent(s)/legal guardian(s) will be instructed

to contact the study staff if the participant experiences severe redness or swelling >14 caliper units, severe pain at the injection site, or fever >40.0°C (>104.0°F), or has an emergency room visit or hospitalization.

Participants will return for Visit 2, approximately 1 month (28 to 42 days) after Visit 1. Information will be collected from the participant's parent(s)/legal guardian(s) on AEs, including nonserious AEs, serious AEs (SAEs), and newly diagnosed chronic medical conditions (NDCMCs), and e-diary follow-up (as needed). Concomitant medications used to treat SAEs or NDCMCs occurring after the previous visit will be recorded. Information on vaccines given since the previous visit will also be recorded. Blood will be collected for immunogenicity assessments.

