8.2.1. Participant Electronic Diary

The participant's parent(s)/legal guardian(s) will be asked to monitor and record local reactions, specific systemic events, fever, and antipyretic/pain medication taken for 7 days, each evening following the study vaccination using an e-diary (in a provisioned device or application on a personal device). This allows recording of these assessments only within a fixed time window, thus providing an accurate representation of the participant's experience. Data on local reactions, specific systemic events, fever, and use of antipyretic/pain medication reported in the e-diary will be transferred electronically to the e-diary vendor, where they will be available for review by investigators, their qualified designees, and sponsor staff at all times via an internet-based portal. At intervals agreed to by the vendor and Pfizer, these data will be transferred electronically to Pfizer for analysis and reporting.

The daily e-diary data will not be captured in the CRF. However, if a participant is withdrawn because of prompted events reported in the e-diary, the event(s) should be recorded on the AE page of the CRF, regardless of whether the investigator considers the event(s) to be clinically significant.

The investigator or designee must obtain stop dates for any local reactions or specific systemic events ongoing on the last day that the e-diary was completed. The stop dates should be entered in the CRF.

Investigators (or an appropriately qualified designee) are required to review the e-diary data online at frequent intervals (daily is optimal) to evaluate participant compliance and reported events as part of the ongoing safety review.

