8.2.2.1. Local Reactions

For the first 7 days following the study vaccination (Days 1 through 7, where Day 1 is the day of vaccination), the participant's parent(s)/legal guardian(s) will be asked to assess redness, swelling, and pain at the injection site (left leg [option for Cohort 1 only] or left arm) and to record the symptoms in the e-diary in the evening. Redness and swelling will be measured and recorded in measuring device (caliper) units (range: 1 to >14; an entry in the e-diary of 15 will denote >14), and then categorized during analysis as mild, moderate, or severe based on the grading scales in [Table 1](#) below. Measuring device units can be converted to centimeters according to the following scale: 1 measuring device unit = 0.5 cm. Pain at the vaccine injection site will be assessed by the participant's parent(s)/legal guardian(s) as mild, moderate, or severe according to the grading scales in [Table 1](#) below. The participant's parent(s)/legal guardian(s) will be prompted to contact the investigator if the participant experiences a severe (Grade 3 or above) local reaction to assess the reaction and perform an unscheduled assessment or visit as appropriate.

Only an investigator is able to classify a participant's local reaction as Grade 4, after physical examination of the participant or documentation from another medically qualified source (eg, emergency room or hospital record). If a participant experiences a Grade 4 local reaction, the investigator must immediately notify the sponsor. Site staff will educate the participant's parent(s)/legal guardian(s) regarding signs and symptoms that would prompt site contact.

The procedure for notification of the sponsor is provided in the ISF or equivalent.

Table 1. Grading Scales for Local Reactions in Study Participants

Local Reaction	GRADE 1 Mild	GRADE 2 Moderate	GRADE 3 ^a Severe	GRADE 4 ^b
Redness	1 to 4 caliper units (or measuring device units) = >0 to 2.0 cm	5 to 14 caliper units (or measuring device units) = >2.0 to 7.0 cm	>14 caliper units (or measuring device units) = >7.0 cm	Necrosis or exfoliative dermatitis ^b
Swelling	1 to 4 caliper units (or measuring device units) = >0 to 2.0 cm	5 to 14 caliper units (or measuring device units) = >2.0 to 7.0 cm	>14 caliper units (or measuring device units) = >7.0 cm	Necrosis ^b

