Pain at injection site (tenderness)	Cohort 1: Hurts if gently touched (eg, whimpers, winces, protests, or withdraws) Cohorts 2-4: Does not interfere with activity	Cohort 1: Hurts if gently touched with crying Cohorts 2-4: Interferes with activity	Cohort 1: Causes limitation of limb movement Cohorts 2-4: Prevents daily activity ^c	Emergency room visit or hospitalization for severe pain (tenderness) at injection site

Abbreviations: CRF = case report form; e-diary = electronic diary.

Note: If the size of the redness and/or swelling falls between 2 measuring device units, the higher measuring device unit number will be recorded in the e-diary.

- Parent(s)/legal guardian(s) of the participants experiencing local reactions >14 caliper units (>7.0 cm) are to be contacted by the study site. An unscheduled visit may be required.
- Grade 4 assessment should be made by the investigator. Grade 4 will not be collected in the e-diary but will be collected as an AE in the CRF. The severity of the local reaction should be graded using the AE grading scale in [Section 10.3.4](#).
- Prevents daily activity, eg, results in missed days of work or school or is otherwise incapacitating.

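### The Visit 1 call instruction defines severe injection site pain by the Cohort 1 criterion for every cohort, but Table 1 uses a different Grade 3 criterion for Cohorts 2-4

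*Protocol*

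**What the plan says.** Protocol 8.10.1 lists three reasons for parents to contact the site during the 7 days after vaccination: fever above 40.0°C, redness or swelling above 14 measuring device units, and "severe injection site pain (causes limitation of limb movement"). The section covers Visit 1 for all cohorts. Within the same sentence the injection site is qualified by cohort, "at the injection site (left leg [option for Cohort 1 only] or left arm) measuring >14 measuring device units", but the explanation of severe pain is not.

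Protocol Table 1 (8.2.2.1) splits Grade 3 pain by age: "Cohort 1: Causes limitation of limb movement Cohorts 2-4: Prevents daily activity". A footnote explains the Cohorts 2-4 criterion by example, as missed work or school or other incapacity. SAP Table 3 (3.1.1.1) has the same split.

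Protocol 8.2.2.1 has parents assess pain "as mild, moderate, or severe according to the grading scales in" Table 1, and says that they "will be prompted to contact the investigator if the participant experiences a severe (Grade 3 or above) local reaction".

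The other parent call instructions give no definition of severe pain. The Synopsis (1.1) asks parents "to contact the study staff if the participant experiences severe redness or swelling >14 caliper units, severe pain at the injection site". The Schedule of Activities footnote (1.3) and Overall Design (4.1) likewise say only that the pain is severe.

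**The concern.** A call instruction should fire at the threshold the protocol uses for severe pain. Here the bracket in 8.10.1 carries the toddler criterion over to children aged 2 to under 18 years, for whom the protocol chose a functional criterion instead. Neither criterion contains the other, so the mismatch can go wrong in both directions.

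What is at stake is the timing of safety follow-up, not the analysis. Under Protocol 8.10.4, a parent's report of severe injection site pain obliges the investigator or a medically qualified designee to make telephone contact as soon as possible and decide whether an unscheduled visit is needed. The same section leaves staff-initiated calls about Grade 3 diary entries optional. The Table 1 footnote under which the site contacts parents is worded for reactions above 14 caliper units, a size measure that does not apply to pain. The parent's own call is therefore the most direct route to a prompt assessment of severe pain.

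**Working it through.** No figure in the plan is in dispute, so the check is a comparison of texts.

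**1. Definition of severe pain by cohort**

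| Cohort | 8.10.1 call instruction | Grade 3 in Protocol Table 1 and SAP Table 3 | Agree? |
|---|---|---|---|
| 1 (15 to <24 months) | limb movement limited | limb movement limited | yes |
| 2 (2 to <5 years) | limb movement limited | daily activity prevented | no |
| 3 (5 to <10 years) | limb movement limited | daily activity prevented | no |
| 4 (10 to <18 years) | limb movement limited | daily activity prevented | no |

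The definitions differ in 3 of 4 cohorts. With 200 children planned per cohort (4.1.2), the wording covers 3 × 200 = 600 of 800 children, or 75%. That is the number to whom the instruction applies, not the number expected to be affected.

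**2. What each mismatch does in Cohorts 2-4**

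- Pain keeps the child from daily activity, but the arm moves: Grade 3 on Table 1, call expected under 8.2.2.1, no call under the bracket in 8.10.1.
- Arm movement is limited, but the child carries on as usual: below Grade 3 on Table 1, call prompted by 8.10.1.

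**3. The other two triggers in the sentence**

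Fever above 40.0°C matches 8.2.2.2.2, and redness or swelling above 14 units matches Table 1. Both thresholds are the same in every cohort. Pain is the only one of the three triggers whose severe grade depends on cohort, and it is given in a single form.

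**4. Whether another section corrects it**

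Four places instruct parents to call and name severe pain: Synopsis 1.1, the Schedule of Activities footnote in 1.3, Overall Design 4.1, and 8.10.1. Only 8.10.1 adds the limb-movement definition (1 of 4). Sections 8.2.2.1 (the general Grade 3 prompt) and 8.10.4 (what the site does after a report) are a different kind of statement and are not counted. None of these texts overrides the bracket for Cohorts 2-4.

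**5. Whether it can be read as Cohort 1 only, or as an example**

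Section 8.10.1 labels cohort-specific steps where they apply, such as blood volume and the leg injection site, so an unlabelled statement applies to all cohorts. The bracket is not introduced as an example, whereas the next bullet in 8.10.1 does mark its examples as such.

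**The case against.** The strongest reply is that the trigger is severe pain, that severity is defined once, in Table 1, and that a stray bracket does not displace the definition. Section 8.2.2.1 gives the cohort-specific rule, and 8.10.4 sends staff back to the 8.2.2 grades when they assess pain. A parent in Cohorts 2-4 whose child cannot carry on daily activity would record severe pain in the diary that evening and fall under the Grade 3 prompt. Investigators or their designees "are required to review the e-diary data online at frequent intervals (daily is optimal"), and 8.10.1 itself repeats that a qualified person "reviews the e-diary data online at frequent intervals for the 7 days following vaccination". An unnecessary call costs only a telephone conversation. Arm pain bad enough to keep a child from school may often limit the arm too. Finally, the diary text and parent handouts are not among the documents, so what parents actually read or hear is unknown.

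Most of this stands as an argument about size. The backstops make a missed case unlikely, and the extra calls are harmless. The overlap between the two criteria is plausible but undocumented, as is any gap between them. None of it makes the two texts agree. Section 8.10.1 is the procedure staff follow when they instruct parents, and in Cohorts 2-4 it gives them the wrong criterion. That the parent materials cannot be seen is a reason to check them.

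**Conclusion.** The concern holds as a minor internal inconsistency. In Cohorts 2, 3 and 4, the severe-pain threshold in the 8.10.1 call instruction is not the Grade 3 threshold in Protocol Table 1 and SAP Table 3. This conclusion rests only on the wording of the two documents.

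The consequence is small. No endpoint, estimand or analysis is touched, because SAP 3.1.1.1 derives maximum pain severity from the e-diary grades on the cohort-specific scale. The effect is limited to whether and when some parents telephone the site, and the diary prompt and site review reduce it further. How many children would have pain that meets one criterion but not the other cannot be estimated from the documents.

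**What to change.** In Protocol 8.10.1, replace the bracket after severe injection site pain with the cohort-specific criteria, "Cohort 1: Causes limitation of limb movement Cohorts 2-4: Prevents daily activity", followed by a reference to Table 1. Then check that any parent-facing Visit 1 instructions, including diary prompts if they define severe pain, use the same two criteria.

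The cost is one bracket and one check of the parent materials. The text change can go into the next protocol amendment with its usual IRB/EC review (10.1.1). Data collection, grading scales, the SAP and the sample size stay as they are.
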